6.5 Missing values, abnormal values and outlying values

For possible missing data in the study process, the missing of primary efficacy endpoints will be carried forward only in principle during the analysis. LOCF (Last Observation Carry Forward) was used as sensitivity analysis for the missing of primary efficacy endpoints. That is, the last observed value is used to replace the missing value. In the sensitivity analysis of the LOCF, the last observed value is "Nonunion of fracture " unless the fracture union is definitive. Other missing indicators will not be carried forward and will be directly analyzed based on the actually observed data. Error and unreasonable data will be processed in the data cleaning process before statistical analysis. For withdrawal of subjects, this part of patient information will still be included in the final statistical analysis. Specific reasons for discontinuation or withdrawal of all patients will be explained in detail in the statistical report, and the missing primary endpoint due to early withdrawal will be analyzed according to the above strategy for processing missing values.

If the date (MMDDYYYY) of collection (non-CEC review data) during the trial is filled in with "UK" or "NA", no treatment will be done.

6.6 Significant level and statistical analysis software

For the primary endpoint, statistical analysis will be performed at the one-sided 0.025 significance level (corresponding to the one-sided confidence limit of the 95% confidence interval). For other endpoints, all statistical analysis will be performed at the two-sided 0.05 significance level (except for special instructions). SAS[®] 9.4 statistical software will be used for statistical analysis.

6.7 Site merging principle

This trial is to be conducted simultaneously in multiple clinical trial institutions, and the actual number of subjects successfully included in each site will vary. In order to avoid the influence of too few actual number of subjects successfully enrolled in the site on the stability and reliability of the primary endpoint analysis results, the sites with the actual number of subjects successfully enrolled less than 10 will be merged. According to previous experience and reference, site merging generally adopts the following two methods:

- Sort the sites with the number of subjects actually enrolled less than 10 according to the site number, and merge the sites directly until the number of subjects in the sites is ≥10 after merging;
- (2) Merge the sites according to the principle of geographical proximity, and the number of subjects in the sites should be ≥ 10 after merging;

The site merging principle adopted in the statistical analysis will be further determined by the sponsor, the investigator and the statistician through a blind review meeting.

7. Statistical Analysis Indicators and Statistical Analysis Methods

7.1 Demographic indicators and other baseline indicators

Demographic data include gender, age, height, weight and BMI; other baseline indicators include the subject's medical history, SF-12v2 questionnaire, EQ-5D questionnaire and preoperative fracture status.

Where:

Age = (Date of informed consent - Date of birth)/365.25;

BMI = Body weight $(kg)/(\text{Height }(m))^2$.

The indicators in this part are mainly descriptive. Enumeration data are described by frequency and composition ratio, while measurement data are described by mean, standard deviation, median, quartile, maximum and minimum. The likelihood ratio Chi-square test will be used to compare the enumeration data between groups. Fisher's exact probability test will be used when the theoretical frequency in the fourfold table is less than 5.

7.2 Intraoperative information

The intraoperative information includes the subject's operation time, blood loss volume, blood transfusion volume, investigational device use, intraoperative fracture, etc.

The indicators in this part are mainly descriptive. Statistical analysis methods are the same as those in 7.1.

7.3 Primary endpoint

The primary endpoint is the fracture union rate 24 weeks after surgery.

Fracture union success is a composite endpoint; in order for an individual subject's surgery implanted with TFNA or PFNA-II to be considered successful he/she must satisfy all of the following criteria:

- 1. No focal tenderness or lengthwise percussion pain, or abnormal movement
- 2. The frontal/lateral X-ray examination shows the vague or no fracture gap, or the continuous callus passing across the fracture line
- 3. No deformation or breakage is found in the investigational product

Calculation principle: Based on the postoperative 24-week follow-up of the fracture status and the X-ray examination results of the fracture site, the calculation principle is as follows:

- 1. It is determined as 'Yes' when the focal tenderness, lengthwise percussion pain and abnormal activity at the postoperative 24-week follow-up of the fracture are filled as 'NA', 'NA' and 'No', respectively;
- 2. It is determined as 'Yes' when the X-ray examination at the fracture site 24 weeks after surgery shows that the fracture line is 'vague' or 'disappeared'; or that the frontal/lateral X-ray examination shows the continuous callus passing across the fracture line is filled as 'Yes';
- ③. It is determined as 'Yes' when the X-ray examination at the fracture site 24 weeks after surgery shows that the implant is filled as 'good';

If (1), (2) and (3) are determined as 'Yes', then the successful fracture union 24 weeks after surgery is determined as 'Yes'; if one of them is missing, it is determined as missing, that is, 'loss to follow-up during the trial'; others are determined as 'No';

For the primary endpoint, the analysis bases on the actual data (except missing data). LOCF (Last Observation Carry Forward) was used as sensitivity analysis for the missing of primary efficacy endpoints. The below 2 analysis tests will be used for the above analysis, and estimates of the differences in efficacy between the groups and bilateral two-sided 95% confidence interval will be given:

(1) CMH chi-square test with adjusted central effects;

Calculation method for non – inferiority P value:

Se=(Rate difference 95% upper limit of confidence interval - Rate difference 95% low limit of confidence interval)/2/ probit (1-0.05/2);

Z=(Investigational group-control group of difference in fracture union rates- non-inferiority margin)/Se;

P value=1-probnorm(Z);

(2) Continuous correction Newcombe-Wilson for non-adjusted central;

The result from test (1) will used for the primary analysis result, the result from test (2) will be used as sensitivity analysis result. If the lower limit of the bilateral two-sided 95% confidence interval on differences in efficacy between the study group and the control group (equal to the lower limit of unilateral 95% confidence interval) is greater than -10%, it can be considered that the investigational product is not inferior to the control product

If the actual study results show that other baseline variables (such as age and gender) are significantly different between the study group and the control group, it will be fully communicated to the investigator in the data analysis stage. Based on the results of univariate analysis for baseline variables and primary endpoint, previous literature references and the clinical expert experience, the indicators affecting the primary endpoint to cause imbalance between groups, i.e., confounding factors, will be further specified. These indicators will be considered into the generalized linear model for correction and included into the sensitivity analysis of the primary endpoint analysis.

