1.2. Investigational Device Description

1.2.1 TFNA

The investigational device is the Trochanteric Fixation Nail Advanced (TFNA; see Figure 1).

Figure 1. Synthes Trochanteric Fixation Nail Advanced (TFNA)

The TFNA nails are cannulated for insertion over a guide wire. A proximal bend of 5° towards lateral allows for an insertion point close to the tip of the greater trochanter. The nail is inserted through the standard lateral surgical approach, which is a straight lateral incision, splitting the iliotibial tract, and gently elevating the vastus lateralis muscle [2]. The entry point is located in the area of the tip of the greater trochanter. Nail insertion and locking of the nail is a well-known procedure that is standard for most medullary nailing systems.

Due to the anatomy of the femur, all nails except for the shortest two lengths are specific for left and right use. The nails are curved in the sagittal plane. The radius of the TFNA follows the anteroposterior curvature of the femur. The TFNA nails are available in different diameters and lengths to match the geometry of the medullary canal. They involve three different caput-collum-diaphyseal (CCD) angles to match the patients'

anatomy. Moreover, the nails are tapered distally to reduce potential stress risers at the distal end of the nail, as secondary fracture around the implant is a typical complication of trochanteric nailing [6, 7].

Distal locking options include one oval locking hole for short nails and three distal locking options for long nails (proximal & distal round locking hole, middle oval locking hole). Both short and long nails incorporate an oval hole allowing for static and dynamic locking. Secondary dynamization is a well-known procedure that reduces the stress exerted by the locking nail [8], leads to greater contact pressure at the fracture site [8], and shortens mean time to union [9]. The method therefore is suitable for fractures with a high risk of delayed healing [2].

An internal locking mechanism prevents the head element from rotating. Sliding may be locked as an option. Highly comminuted fractures may be a good candidate for locked fixation. As an option, the proximal fragment can be re-approximated with a specific intraoperative compression feature, which is a standard feature seen in many proximal femoral nailing devices (e.g. PFNA or Stryker Gamma3).

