5.0 ENDPOINTS

5.1. Primary Endpoint

The primary endpoint is fracture union at 24 weeks postoperatively. Fracture union success is a composite endpoint; in order for an individual subject's surgery implanted with TFNA or PFNA-II to be considered successful he/she must satisfy all of the following criteria at 24 weeks:

- 1. No focal tenderness or lengthwise percussion pain, or abnormal movement
- 2. The frontal/lateral X-ray examination shows the vague or no fracture gap, or the continuous callus passing across the fracture line
- 3. No deformation or breakage is found in the test product

The primary endpoint analysis will be to demonstrate that the investigational device (TFNA) is non-inferior to the control device (PFNA-II) based the fracture union rate at the 24 week follow-up visit. Non-inferiority test will be conducted based on a one-sided 97.5% confidence interval for the difference in the fracture union rates at 24 weeks between the investigational and control groups.

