5.2. Secondary Endpoints

The following secondary endpoints will be evaluated:

- Adverse events (type and frequency) for all adverse events will be compared for the investigational and control groups
- 24-week revision rate where revision is defined as removal of any component for any reason.
- 24-week reoperation rate is defined as secondary surgery at the fracture site(s) for any reason
- Clinical Outcomes
 - o SF-12
 - Harris Hip Score
 - o EQ-5D
- Radiographs: incidence of complications such as loosening or cut-out that require reoperation or revision

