8.5. Reporting an Adverse Event

Adverse events are reported from the start time of the index procedure until the subject's study participation has ended (i.e. revision, completion of study or withdrawal of consent). All AEs must be followed until the AE has resolved, stabilized, or the study has been completed.

The Investigator will record the nature, severity, treatment and outcome of the AE, and will

determine the relationship to the investigational products, medications or any protocol mandated procedures involved in the clinical study.

The following categories of adverse event severity are to be used:

Mild:	Awareness of sign or symptom that does not interfere with the subject's
	usual activity or is transient, resolved without treatment and with no
	sequelae,
Moderate:	Interferes, but does not hinder, the subject's usual activity and may
	require treatment,
Severe	Symptom(s) causing severe discomfort and significant impact on the
	subject's usual activity and requires treatment or intervention.

The causal relationship should be rated as follows:

Unrelated:	The event is definitely not associated with product application
Unlikely:	The temporal sequence between product application and the event is such that the relationship is unlikely,
Possible:	The temporal sequence between product application and the event is such that the relationship is not unlikely or the subject's condition or concomitant therapy could have caused the AE,
Probable:	The temporal sequence is relevant or the event abates upon product application completion or the event cannot be reasonably explained by the patient's condition,
Related:	The temporal sequence is relevant and the event abates upon product application completion or reappearance of the event on repeat product application (re-challenge).

Adverse events will be reported by the investigator to the Sponsor via the CRF.

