10.8. Analysis Sets

All subjects who met the inclusion and exclusion criteria will be eligible for enrollment and will be randomized to either the investigational (TFNA) or the control (PFNA-II) group. The following two analysis sets have been defined for this study:

1) Intent-to-Treat (ITT) Population

This analysis set includes all subjects randomized and implanted with a protocol specified implant, TFNA or PFNA-II. It includes the patients who were treated and withdrew prior to

week 24 due to various reasons. If a patient is randomized to one treatment group, but receives the other group for any reasons, the patient is considered to be part of the treatment group as received. This analysis set will be the primary one for the secondary safety analysis.

2) Per Protocol Population

The Per Protocol Population will consist of the subset of the ITT Population who complete 24 weeks of follow-up with no major protocol deviations (including but not limited to: failure to satisfy all inclusion/exclusion criteria, failure to adhere to all protocol-required restrictions and prohibitions, receipt of prohibited concomitant procedures or therapies, and non-compliance to protocol-specific procedures) as determined by a review of subject data.

This PP population will be the analysis set for conducting the primary and secondary effectiveness endpoint analyses.

Separately from these two populations, any subjects who are enrolled into the study but who do not receive one of the study devices will be summarized separately. This summary will include demographics and reasons for not receiving a study device.
The figure below illustrates these populations:

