6.2 Sample size calculation

The sample size calculation is determined based on the primary endpoint using PROC POWER in SAS software version 9.3. It assumes that the fracture union rate at 24 weeks after surgery in the TFNA group would be equivalent to that of the PFNA-II group, and a common fracture union rate is approximately 95% or greater based on the literature review. With a non-inferiority margin of 0.10 and a power of 80%, this implies a sample size of 75 for the TFNA and of 75 for PFNA-II surgery groups, respectively. The sample size will be increased to 188 (94 per group) to accommodate potential 20% attrition.

The sample size applies to patients enrolled, randomized, and actually treated. Some patients who enroll in a study and are randomized may not be ultimately treated for various reasons. Patient enrollment and randomization will continue until the proposed sample size for treated patients is complete.

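### The primary endpoint reads only the week-24 state, so a subject revised earlier for fixation failure can leave the deciding analysis or score as a success

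*SAP*

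**What the plan says.** Protocol 5.1 requires that the subject "he/she must satisfy all of the following criteria at 24 weeks": the clinical signs, the X-ray finding, and an intact implant. SAP 7.3 turns this into a derivation "Based on the postoperative 24-week follow-up of the fracture status and the X-ray examination results of the fracture site". The implant component passes when the implant is recorded as good on the week-24 film. Neither document says how an earlier revision, reoperation or breakage is scored.

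Three further rules determine what happens to a revised subject.

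- **Follow-up.** Protocol 8.5 reports adverse events "until the subject's study participation has ended (i.e. revision, completion of study or withdrawal of consent", so revision is named as an end of participation. Protocol 9.2 encourages every subject to stay to week 24, and the reasons for discontinuation in 9.1 (not an exhaustive list) do not include revision.
- **Missing components.** In SAP 7.3 one missing component makes the endpoint missing and labels it loss to follow-up. SAP 6.4 subtracts loss to follow-up from the PPS. The protocol's per-protocol set takes subjects "who complete 24 weeks of follow-up with no major protocol deviations", and protocol 10.10.5 analyses only known outcomes.
- **Where revision is counted.** It is a secondary endpoint, the "24-week revision rate where revision is defined as removal of any component for any reason". SAP 7.4 treats it, and reoperation, as mainly descriptive.

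LOCF, with nonunion as the default unless union was definitive, is a sensitivity analysis.

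**The concern.** Take a subject whose implant cuts out at week 8 and is exchanged.

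- **Path (a).** Participation ends at revision. There is no week-24 form, so the endpoint is missing. A device failure is filed as attrition and leaves the PPS and the observed-data FAS estimate.
- **Path (b).** The subject stays. If the re-fixed fracture has united and the replacement implant is good, the derivation returns success for the arm whose first fixation failed. The week-24 data are complete, so no missing-data method reaches this case.

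In both paths early failures disappear from the comparison and both arms move toward full success. If TFNA had more early failures than PFNA-II, the observed difference would shrink toward zero, which in a non-inferiority trial favours the claim. Which path applies may also vary by site, because 8.5 and 9.2 point different ways.

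**Working it through.** **The plan's own figure.** The inputs from SAP 6.2 and 6.6 are 95% union in both arms, margin 0.10, 80% power, and testing where "statistical analysis will be performed at the one-sided 0.025 significance level".

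n = 2 × 0.95 × 0.05 × (1.960 + 0.842)² / 0.10² = 74.6, so 75 per arm. 75 / 0.80 = 93.75, so 94 per arm and 188 in total. The planned size is right for its inputs; the fault is in the endpoint rule.

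**One data set (illustration).** 94 per arm; 10 TFNA subjects revised early, none on control; 80 of the 84 unrevised TFNA subjects and 89 of 94 controls united. Wald lower limit = d − 1.96 × √(p₁q₁/n₁ + p₂q₂/n₂).

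| Scoring of the 10 | TFNA v PFNA-II | Difference | Lower limit, Wald | Lower limit, Newcombe (continuity-corrected) |
|---|---|---|---|---|
| Missing | 80/84 v 89/94 | +0.6 | -5.9 | -7.8 |
| Success | 90/94 v 89/94 | +1.1 | -5.0 | -6.6 |
| Failure | 80/94 v 89/94 | -9.6 | -18.1 | -19.3 |

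The first two rows meet the -10% criterion and the third does not. LOCF on the FAS gives the third row if none of the ten had definitive union recorded before revision.

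**Repeated trials.** Inputs: 94 analysed per arm with no other loss; revision 16.5% (TFNA) and 6.5% (PFNA-II); union in unrevised subjects 95% (the plan's rate) or 97%; union at week 24 among revised subjects who stay, 50% or 80%. The 6.5% is the PFNA-II reoperation rate in protocol Table 4. The 16.5% and the post-revision union rates are assumptions. With revision counted as failure, the true difference is 0.95 × (0.835 − 0.935) = -9.5 points, or 0.97 × (0.835 − 0.935) = -9.7 points.

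Share of 200,000 simulated trials with the lower limit above -10%, continuity-corrected Newcombe / Wald:

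| Scoring of revised subjects | 95% union | 97% union |
|---|---|---|
| Dropped | 65% / 83% | 78% / 94% |
| Week-24 state, 80% united | 50% / 66% | 56% / 77% |
| Week-24 state, 50% united | 18% / 25% | 18% / 28% |
| Failure | 2% / 3% | 2% / 3% |

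With 75 per arm and 95% union, the dropped row becomes 50% / 75%. Wald stands in for the site-adjusted CMH analysis, which cannot be reproduced without site sizes.

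**Power if revisions count as failures and the devices are equal.** The common success rate is 0.95 × (1 − r). At r = 2% it is 0.931, which needs 101 evaluable per arm by the formula above. At r = 6.5% it is 0.888, which needs 156. With 94 analysed per arm (simulation, Wald), power is about 78% at 2% and 59% at 6.5%, against about 86–87% if revised subjects are dropped.

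**The case against.** **Existing safeguards.** LOCF scores most path (a) subjects as nonunion, and SAP Table 30 gives it its own interval and non-inferiority P value. Revision and reoperation rates are tabulated with between-group P values on the FAS and PPS, so an excess would be seen. This stands as a reason why path (a) would usually come to light. But SAP 7.3 labels LOCF a sensitivity analysis. The SAP tables show it on the FAS only, and the protocol's version (10.5, 10.10.6) is on a per-protocol set that already requires completed follow-up. It can carry forward a union recorded before a later failure, and it cannot reach path (b). The complication endpoint in SAP 7.4(5) does not help as written: it codes a revised or reoperated subject as missing and everyone else as no.

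**Magnitude.** The documents give no TFNA excess; protocol 2.0 and 2.2 expect similar risk. The 6.5% comes from one randomised trial with 47 PFNA-II subjects and is not stated to be a 24-week rate; nor are the range maxima in Table 2. Union was reported in all 389 PFNA-II subjects for whom it was given. This stands in full: the percentages are conditional illustrations.

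**Paths.** For any one subject the two paths are alternatives, and 8.5 sits in an adverse-event reporting section. Path (a) has the more direct textual support; path (b) needs continued follow-up.

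**Remedy.** The objective is union. Scoring every component removal as failure would fail a united fracture after elective screw removal, and lower power. That stands, and it narrows the fix.

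**Conclusion.** The gap is real. It is a stated derivation rule, not a detail left open: followed exactly, it takes some failures of fixation out of the deciding analysis and can credit others as successes. Under the assumed 16.5% v 6.5% revision, a device about 9.5 to 9.7 points worse is declared non-inferior in about 65–94% of trials (dropped) or 18–77% (week-24 state), where counting failures gives 2–3%. If early revision is rare or equal in the arms, the distortion is small.

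Three stronger readings are not supported.

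- A reader might infer that every early revision is lost or credited. It is not: a revised subject who attends week 24 ununited, tender, or with an implant not recorded as good is scored as a failure.
- A reader might infer that TFNA is expected to fail early more often, or that the literature rates give the size of the bias. The documents say neither.
- A reader might infer that secondary dynamization automatically counts as revision, since protocol 1.2.1 says "The method therefore is suitable for fractures with a high risk of delayed healing". No passage says that it involves removing a component.

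**What to change.** In protocol 5.1 and SAP 7.3, state that a subject is not successful, whatever the week-24 findings, after a revision or a reoperation at the fracture site on or before the week-24 assessment that is recorded as due to any of these: implant breakage or deformation; cut-out, loosening or migration; loss of reduction; delayed union or nonunion. State also that such a subject is not loss to follow-up and stays in the FAS and PPS.

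Add a sensitivity analysis that counts every revision or reoperation, for any reason, as failure. It shows how far the result depends on the recorded cause, which is assigned by unblinded staff.

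Reconcile protocol 8.5 with 9.2 on whether follow-up continues after revision.

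**Cost.** The text is short, and SAP 7.4(2)–(3) already derive revision and reoperation with dates from the adverse-event records; cause would have to be classified from the same records by a rule set in advance. The real cost is power. The success rate falls, so restate power at the resulting rate: about 78% at 2% and 59% at 6.5% qualifying revision in both arms (94 analysed, 95% union if unrevised, Wald). For 80% power the formula needs 101 or 156 evaluable per arm, that is 101 / 0.80 → 127 or 156 / 0.80 = 195 enrolled per arm.

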10.10.5 Analysis of the primary endpoint

In accordance with ICH guidance E9(²)the primary endpoint analysis will be based on the Per-Protocol set of patients for a comparison of the fracture union rates at Week 24 between TFNA and PFNA-II. Only patients in this analysis set with a known outcome for the primary endpoint will be analyzed.

The null hypothesis (TFNA is inferior to PFNA-II) will be rejected, and TFNA will be considered non-inferior to PFNA-II if the exact 97.5% upper one-sided confidence bound for the difference in fracture union rates between PFNA-II and TFNA at 24 weeks is less than non-inferiority margin, 10.0%.

Two sub-components of the primary endpoint at 24 weeks (radiographic outcome, and no deformation or breakage) will be compared between the two treatment groups.

Radiographic outcome, i.e. front/lateral X-ray films, will be assessed by the independent radiographic reviewer to determine if there are vague or fracture gap or continuous callus passing across the fracture line. The radiographic outcome will be summarized and compared at each follow up visit between the two treatment groups using Fishers exact test.

Similarly, the independent radiographic reviewer will also determine whether deformation or breakage of the implant has occurred. This outcome will be summarized between the two treatment groups at each follow up visit, as well.

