2.3 Primary endpoint

The primary endpoint is the fracture union rate 24 weeks after surgery. Fracture union success is a composite endpoint; in order for an individual subject's surgery implanted with TFNA or PFNA-II to be considered successful he/she must satisfy all of the following criteria:

- 1. No focal tenderness or lengthwise percussion pain, or abnormal movement
- 2. The frontal/lateral X-ray examination shows the vague or no fracture gap, or the continuous callus passing across the fracture line
- 3. No deformation or breakage is found in the investigational product

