Number of subjects (N miss)	XXX (XXX)	XXX (XXX)	X.XXXX	X.XXXX
Stable	XXX (XX.X%)	XXX (XX.X%)		
Loss of reduction	XXX (XX.X%)	XXX (XX.X%)		
Is the re-operation required				
Number of subjects (N miss)	XXX (XXX)	XXX (XXX)	X.XXXX	X.XXXX
Yes	XXX (XX.X%)	XXX (XX.X%)		
No	XXX (XX.X%)	XXX (XX.X%)		
Implant				
Number of subjects (N miss)	XXX (XXX)	XXX (XXX)	X.XXXX	X.XXXX
Good	XXX (XX.X%)	XXX (XX.X%)		
Rupture of screw/bolt	XXX (XX.X%)	XXX (XX.X%)		
Rupture of intramedullary nail	XXX (XX.X%)	XXX (XX.X%)		
Displacement of screw/bolt	XXX (XX.X%)	XXX (XX.X%)		
Displacement of intramedullary nail	XXX (XX.X%)	XXX (XX.X%)		
Fracture line	VVV (VVV)	VVV (VVV)	V VVVV	v vvvv
Number of subjects (N miss)	XXX (XXX)	XXX (XXX)	X.XXXX	X.XXXX
Clear	XXX (XX.X%)	XXX (XX.X%)		
Vague	$\begin{array}{c} XXX (XX.X\%) \\ XXX (XX V\%) \end{array}$	$\begin{array}{c} XXX (XX.X\%) \\ XXX (XX Y\%) \end{array}$		
Disappeared Callus	XXX (XX.X%)	XXX (XX.X%)		
	VVV (VVV)	VVV (VVV)	X.XXXX	X.XXXX
Number of subjects (N miss) NA	XXX (XXX)	XXX (XXX)	Λ.ΛΛΛΛ	Λ.ΛΛΛΛ
Intermittent	XXX (XX.X%)	$\begin{array}{c} XXX (XX.X\%) \\ YYY (YY Y\%) \end{array}$		
Continuous	XXX (XX.X%) XXX (XX.X%)	XXX (XX.X%) XXX (XX.X%)		
The frontal/lateral X-ray examination	· · · · ·	· · · · ·	and the free stur	lina
Number of subjects (N miss)		XXX (XXX)	X.XXXX	X.XXXX
Yes	XXX (XXX) XXX (XX.X%)	$\begin{array}{c} \text{XXX} (\text{XX.X\%}) \\ \text{XXX} (\text{XX.X\%}) \end{array}$	Λ.ΛΛΛΛ	Λ.ΛΛΛΛ
No		· · · · ·		
	XXX (XX.X%)	XXX (XX.X%)		
Determine the fracture union condition		VVV (VVV)	v vvvv	V VVVV
Number of subjects (N miss)	$\begin{array}{c} XXX (XXX) \\ YYY (YY Y0) \end{array}$	XXX (XXX)	X.XXXX	X.XXXX
No union	XXX (XX.X%)	$\begin{array}{c} XXX (XX.X\%) \\ YYY (YY Y\%) \end{array}$		
Union	XXX (XX.X%)	XXX (XX.X%)		

Table 73Statistical analysis results of subjects' x-ray examination at the
fracture site 24 weeks after surgery

Notes: 1. The likelihood ratio Chi-square test or Fisher's exact probability test is used to analyze the intergroup comparison of qualitative indicators;

2. Investigational device: Trochanteric Fixation Nail Advanced (TFNA); control device: Proximal Femoral Nail Antirotation (PFNA-II);

T 1' /				
Indicator	Study group	Control group	Statistics	P value
White blood cell (WBC)				
Number of subjects (N miss)	XXX (XXX)	XXX (XXX)	X.XXXX	X.XXXX
Normal \rightarrow Abnormal (with clinical significance)	XXX (XX.X%)	XXX (XX.X%)		
Normal \rightarrow Abnormal (without clinical significance)	XXX (XX.X%)	XXX (XX.X%)		

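### SAP 7.3 fails criterion 3 of the primary endpoint for any implant not rated good, so an intact but displaced implant is scored as a union failure against the endpoint's own definition

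*SAP*

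**What the plan says.** Protocol 5.1 gives the third criterion of the composite as "No deformation or breakage is found in the test product". SAP 2.3 repeats it as "No deformation or breakage is found in the investigational product", and SAP 7.3 opens with the same definition.

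The calculation principle in SAP 7.3 then makes it operational. Criterion 3 is met when the 24-week X-ray "shows that the implant is filled as 'good". If any component is missing, the composite is missing. If all three are met, it is a success. For the rest, "others are determined as 'No".

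SAP Table 73 shows the values of the 24-week implant field: good, rupture of screw/bolt, "Rupture of intramedullary nail", "Displacement of screw/bolt" and "Displacement of intramedullary nail". Tables 58, 63 and 68 list the same five for weeks 1, 6 and 12.

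Protocol 10.10.5 says that "the independent radiographic reviewer will also determine whether deformation or breakage of the implant has occurred", and asks for this sub-component to be compared between arms at 24 weeks. Protocol 5.2 places loosening and cut-out in a separate secondary endpoint, limited to events that need reoperation or revision.

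**The concern.** The definition and the derivation classify the same patient differently. A screw or nail that has moved but is neither bent nor broken meets the written criterion and fails the scoring rule. This happens inside SAP 7.3, where definition and rule stand a few lines apart, so a programmer following one and a reader following the other would count different successes.

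A second gap is less certain. The definition names deformation, but no listed value denotes it, and SAP 7.3 does not name the independent reviewer's determination as its source.

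This variable decides the trial. If displacement enters the composite, the 95% success rate behind the sample size no longer describes what is analysed. A difference in displacement between the devices could also offset or imitate a difference in union.

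**Working it through.** **1. Definition against rule, by value of the Table 73 implant field**

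| Field value | Definition (protocol 5.1, SAP 2.3, SAP 7.3) | SAP 7.3 rule |
|---|---|---|
| Good | met | met |
| Rupture of screw/bolt | not met | not met |
| Rupture of nail | not met | not met |
| Displacement of screw/bolt, implant intact | met | **not met** |
| Displacement of nail, implant intact | met | **not met** |
| Deformation | not met | no value listed |

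Two of the four values other than good are scored against the definition. This rests on wording alone.

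**2. The plan's own figure**

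Inputs (protocol 10.9, SAP 6.2): success 95% in both arms, margin 0.10, power 80%. The synopsis gives a one-sided alpha of 2.5%.

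n = (1.96 + 0.8416)² × 2 × 0.95 × 0.05 / 0.10² = 74.6, so 75 per arm. Then 75 / 0.80 = 93.75, so 94 per arm and 188 in total. Both stated figures reproduce.

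Power = Φ(0.10 / √(2p(1−p)/n) − 1.96). At p = 0.95 and n = 75 this is Φ(0.10/0.0356 − 1.96) = 80.2%.

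**3. Power if displacement counts as failure (illustration)**

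The documents give no displacement rate for this trial. The nearest figure is literature migration: 0.0% to 9.1% across nails in protocol Table 2, and 8.7% for PFNA-II in Table 4. It is only a proxy. Assume a displacement rate d equal in both arms and independent of union, so p = 0.95 × (1 − d), with 75 per arm:

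| d | p | Power |
|---|---|---|
| 0% | 95.0% | 80% |
| 1% | 94.1% | 74% |
| 2% | 93.1% | 68% |
| 5% | 90.3% | 54% |
| 8.7% | 86.7% | 44% |
| 9.1% | 86.4% | 43% |

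Independence matters. At d = 8.7% with maximum overlap, where all of the 5% non-unions are also displaced, p = 1 − 0.087 = 91.3% and power is 58%.

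**4. Error at the boundary (illustration)**

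Take true union of 85% (TFNA) and 95% (PFNA-II), 75 per arm, again independent of displacement. The scored difference is 0.85(1 − d_TFNA) − 0.95(1 − d_PFNA-II). The chance of declaring non-inferiority is Φ((0.10 + difference)/SE − 1.96), where SE = √(p_T(1−p_T)/75 + p_C(1−p_C)/75).

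| Displacement, TFNA / PFNA-II | Scored difference (points) | Chance of declaring non-inferiority |
|---|---|---|
| 0% / 0% | −10.0 | 2.5% |
| 2% / 2% | −9.8 | 2.7% |
| 4% / 4% | −9.6 | 3.0% |
| 8.7% / 8.7% | −9.1 | 3.4% |
| 4% / 8.7% | −5.1 | 13% |
| 8.7% / 4% | −13.6 | 0.5% |

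The 4% is an assumption with no source in the documents.

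**The case against.** The strongest reply concerns reach and size. The displacement mismatch itself has no answer in the text.

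- **Deformation.** A reader might infer that the trial cannot detect deformation, or that bent implants will be entered as good. The documents do not show this. The CRF is not among them, the five values come from output shells, and protocol 10.10.5 has the independent reviewer judge deformation. A bent nail is also not naturally rated good. What stands is narrower: the SAP rule and shells carry no deformation value and do not use the reviewer's determination.
- **Power.** A reader might take 44% as the expected power. It rests on one cited trial arm of 47 patients and on independence. Table 4 gives 0.0% migration for the other nail in that trial, and some displaced implants would already fail on pain, movement or X-ray union. Only a range is defensible.
- **Type I error.** A reader might infer that false non-inferiority rises to 13%. That needs an unsourced TFNA rate below half of the control's. Equal rates give 2.7% to 3.4%, and the reverse gives 0.5%. Protocol 2.0 expects a similar risk-benefit ratio for the two devices.
- **Visibility.** Table 73 reports displacement by arm, so a result driven by displacement could be noticed. This helps interpretation but leaves the primary variable misclassified.

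**Conclusion.** The point holds for displacement and is wrong as written: the SAP 7.3 rule turns an intact, displaced implant into a union failure, contrary to the definition in protocol 5.1, SAP 2.3 and SAP 7.3. For deformation, the finding is only that the SAP names no value and no source; whether the CRF has one is open.

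The size is not known. Under equal, independent displacement of 1% to 9.1%, power at 75 per arm is 74% to 43% against 80% planned. Overlap with non-union reduces the loss. The effect on the false-positive rate can go either way, so the documents do not support saying that the rule favours TFNA. These figures treat literature migration as a stand-in for the SAP's displacement categories. The sample-size arithmetic is correct for the 95% rate that it assumes.

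**What to change.** In SAP 7.3, fail criterion 3 only for rupture of a screw/bolt, rupture of the nail, or a deformation recorded by the independent radiographic reviewer under protocol 10.10.5, and name that source. Confirm whether the CRF or the reviewer's form has a deformation field, and add one if it does not. Tabulate displacement by arm separately, as Table 73 already does, and keep the good-only scoring as a sensitivity analysis. The secondary complications endpoint is not a substitute home for displacement, because it covers only events that need reoperation or revision.

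If displacement is meant to be a failure, amend the criterion in both documents instead, and restate the 95% planning rate and the power, before database lock.

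The cost is minor SAP rewording and possibly re-coding from existing reads. Correcting the scoring needs no extra patients. Choosing to count displacement would reopen the sample size.
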